Study Protocol and Statistical Analysis Plan

**Study on the Relationship Between Pathological
Features of Achalasia and Prognosis of Per-oral
Endoscopic Myotomy**

**Main research institute: Beijing Friendship Hospital,
Capital Medical University**

Study Director: [name],

Date: April 1st, 2021

Directory

1. Background	3
2. Research objectives	4
3. Research content	4
4. Research proposal	4
5. Data processing and analysis	9
6. Quality control	9
7. References	9

Background

Achalasia is the most common motility disorder of esophagus, characterized by disorders of the lower esophageal sphincter (LES). Normal peristalsis of the esophagus is eliminated and replaced by synchronous or ineffective contraction. Based on high-resolution manometry (HRM), the patients with achalasia were categorized into 3 subtypes, type I: achalasia with minimum esophageal pressurization, type II: achalasia with esophageal compression and type III: achalasia with spasm.

Previous studies have found that the pathological features of the esophageal muscular layers in patients with achalasia are degeneration of nerve plexus, reduction of interstitial cells of Cajal (ICCs), muscular atrophy, fibrosis and infiltration of different inflammatory cells. Different subtypes of achalasia have different clinical characteristics and esophageal motility. Studies have found that ganglion cells in type I patients are significantly reduced compared with type II patients, but the pattern is similar, which may indicate that type I achalasia represents the progression of type II achalasia. Studies have shown that ICCs are preserved in type III achalasia compared with type I and II achalasia. In addition, Achalasia is related to viral infection and autoimmune disease. Nowadays, per-oral endoscopic myotomy (POEM) is a main therapy for patients with achalasia. Most studies have focused on the relationship

between pathological features and motility characteristics of achalasia, but there are few studies on the relationship between pathological features and therapeutic effect of POEM.

This study will evaluate the pathological characteristics of full-thickness esophageal muscle in patients with achalasia in order to discover the relationship between different pathological characteristics and prognosis of POEM.

Research objective

To determine whether there is difference in prognosis of POEM among patients with achalasia of different pathological characteristics.

Research content

This study prospectively collects the information of 50 participants undergoing POEM for achalasia in Beijing Friendship Hospital, Capital Medical University. During POEM, all patients are required to obtain esophageal muscle biopsy for pathological examination. Participants will be followed up by telephone at 1, 3, 6, and 12 months after POEM for improvement in clinical symptoms.

Research proposal

1. Research design

This is a prospective study based on Beijing Friendship Hospital affiliated to Capital Medical University. The data of 50 patients undergoing POEM due to achalasia were prospectively collected,

including demographic data, drug and surgical treatment data during hospitalization. At POEM, all patients are required to obtain esophageal muscle biopsy and mucosal tissue samples for pathological examination. The patients were followed up by telephone at 1, 3, 6, and 12 months for improvement in clinical symptoms.

2. The research object

2.1 Study Population

The subjects of this study were patients undergoing concurrent POEM surgery for achalasia in Beijing Friendship Hospital affiliated to Capital Medical University.

2.2 Number of planned enrollment cases

50 cases.

2.3 Into the discharge standard

Inclusion criteria:

- 1) Patients with achalasia treated in Beijing Friendship Hospital, Capital Medical University
- 2) Age 18-80, no gender limitation
- 3) Fit and agree to receive POEM therapy
- 4) Signed informed consent

Exclusion criteria:

- 1) the previously received treatment of achalasia, Barrett's esophagus lesions, esophageal stricture, liver cirrhosis, and/or

esophageal varices, the digestive tract tumor, active esophagitis, connective tissue disease, allergic disease, blood or blood coagulation patients and hiatal hernia.

2) Use of nonsteroidal anti-inflammatory drugs, corticosteroids, or other immunosuppressive drugs 6 months prior to examination.

3. Research methods

3.1 Diagnosis and classification of achalasia

According to clinical manifestations, endoscopy and high-resolution esophageal manometry, achalasia was diagnosed.

3.1.1 Clinical symptom score

The Eckardt score was used to score clinical symptoms based on preoperative dysphagia, regurgitation, retrosternal pain, and reduced body mass. Doctors need to collect information about the patient's history of viral infections and autoimmunity, such as herpes simplex virus (HSV), varicella zoster, measles, and human papillomavirus (HPV). Autoimmune diseases include urticaria, eczema, ankylosing spondylitis, Hashimoto's thyroiditis, rheumatoid arthritis and sjogren's syndrome.

3.1.2 Endoscopy

All patients underwent endoscopy to exclude tumors, inflammatory reactions or large ulcers in the esophagus and stomach, especially in the lower esophagus or the gastroesophageal junction.

3.1.3 High-resolution manometry

The pressure measurement included resting pressure data, 10 times of swallowing with 5ml water in supine position, and fast swallowing data. The data includes UES, LES, and esophageal body pressure measurement data. Achalasia is divided into three subtypes.

3.2 POEM and muscular pathology

Patients received routine POEM surgery, and full-thickness esophageal muscle biopsy was performed from LES, distal esophagus (about 5cm above EGJ) and middle esophagus (about 10-20cm above EGJ) during the operation. Intraoperative biopsy to take pathological tissue depends on the patient's condition, and the collection method is to use biopsy forceps to take tissue, and take 1 piece at one place.

3.3 Pathological staining and evaluation

Tissue samples were fixed with formalin and embedded in paraffin before sectioning and staining.

3.3.1 Specific dyeing items

- 1) HE staining is used to evaluate the atrophy degree of smooth muscle and the number of inflammatory cells.
- 2) Azan-Mallory staining was used to assess the degree of fibrosis.
- 3) C-KIT immunohistochemistry: C-KIT was positive, and trypsin-like IHC staining was negative to evaluate ICC cells.
- 4) S100: Evaluate the degree of ganglion loss
- 5) The number of eosinophil cells was evaluated by HE staining, MBP

and EDN

- 6) Mast cells: C-kit positive, trypsin-like IHC staining positive.
- 7) Lymphocyte inflammation.

3.4 Follow-up contents

Follow-up data were collected, including symptom relief (Eckardt score), reflux symptom score (GerdQ score), gastroscopic manifestations, reflux esophagitis, esophagography and esophageal manometry. Follow-up collection time is 1 month, 3 months, 6 months and 12 months after POEM. Patients' symptom improvement and postoperative reflux will be inquired.

4. Clinical outcomes

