4.2 Secondary clinical outcomes

Secondary end points were the presence of reflux symptoms (GerdQ score >7) or evidence of reflux esophagitis under endoscopy during follow-up. In addition, we will evaluate pathological differences between different sites to provide evidence for selecting the best biopsy site.

Data processing and analysis

Measurement data are expressed as $x \pm s$ or median, as appropriate,

and count data rate and percentage are expressed. The chi-square test or Fisher's exact test was used to analyze the count data, and the Student's T test or Mann-Whitney test was used to analyze the qualitative and quantitative differences among the subgroups. All P values were bilateral, and P <0.05 was considered as statistically significant difference.

Quality control

In this study, two doctors will participate in patient enrollment, input of baseline data and follow-up data, and jointly check the accuracy and authenticity of data.

References

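### No GerdQ is specified before POEM, so the symptom part of the reflux end point may mix persisting with new symptoms

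*Combined protocol and SAP*

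**What the plan says.** **Before POEM.** Section 3.1.1 provides one symptom score: "The Eckardt score was used to score clinical symptoms based on preoperative dysphagia, regurgitation, retrosternal pain, and reduced body mass". The rest of the work-up in section 3.1 is history of viral infection and autoimmune disease, endoscopy and manometry. The research design section adds a general list, "including demographic data, drug and surgical treatment data during hospitalization". None of these names GerdQ or another reflux score. The quality control section mentions baseline data ("two doctors will participate in patient enrollment, input of baseline data and follow-up data") without listing the items.

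**After POEM.** Section 3.4 introduces GerdQ: "Follow-up data were collected, including symptom relief (Eckardt score), reflux symptom score (GerdQ score), gastroscopic manifestations". The timing is "Follow-up collection time is 1 month, 3 months, 6 months and 12 months after POEM".

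**End point.** Section 4.2 reads: "Secondary end points were the presence of reflux symptoms (GerdQ score >7) or evidence of reflux esophagitis under endoscopy during follow-up". It sets no new-onset condition and no change from baseline.

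**Analysis.** Counts are compared by chi-square or Fisher's exact test, two-sided at 0.05, with no covariate.

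**Entry screen for esophagitis.** The exclusions in section 2.3 include "active esophagitis, connective tissue disease, allergic disease, blood or blood coagulation patients and hiatal hernia", and section 3.1.2 states: "All patients underwent endoscopy to exclude tumors, inflammatory reactions or large ulcers in the esophagus and stomach".

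**The concern.** The objective is to relate pathology to prognosis after POEM. For the symptom part of the reflux end point, prognosis is read from follow-up status alone. Section 2.3 excludes active esophagitis and hiatal hernia but not reflux symptoms, so a patient may enter with GerdQ >7. If the score is still above 7 afterwards, that patient is an event, and nothing specified in the plan shows that the symptom came first.

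Two things follow. The reported rate of reflux symptoms could be a mixture of persisting and new symptoms in unknown proportion. And if pathology is associated with symptoms before POEM, an unadjusted comparison could show a pathology-reflux relation with no difference in new reflux. A baseline score that was not taken cannot be reliably recovered later.

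**Working it through.** **Step 1: the text.** The plan states no figure on this point, so there is none to reproduce. GerdQ occurs in two places, section 3.4 (after POEM only) and section 4.2 (the >7 threshold). The Eckardt score is specified both before POEM (section 3.1.1) and after it (sections 3.4 and 4.1). The endoscopic component has an entry screen (sections 2.3 and 3.1.2). Of these three measures, GerdQ alone has no specified baseline.

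**Step 2: how far the rate could be affected.** All three inputs are assumptions; the documents give none of them.

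- b, proportion with GerdQ >7 before POEM: 10% to 40%
- s, proportion of those still >7 at follow-up: 50%
- q, proportion of the rest who become positive: 20%

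Observed rate = b·s + (1 − b)·q. If patients positive at baseline carried only the same 20% risk as the others, the rate would be q. The part added by baseline status is therefore b·(s − q) = 0.30·b.

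| b | Observed rate | Added by baseline status | Share of positives |
|---|---|---|---|
| 10% | 0.05 + 0.18 = 23% | 3 points | 3/23 = 13% |
| 20% | 0.10 + 0.16 = 26% | 6 points | 6/26 = 23% |
| 30% | 0.15 + 0.14 = 29% | 9 points | 9/29 = 31% |
| 40% | 0.20 + 0.12 = 32% | 12 points | 12/32 = 38% |

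Patients positive both before and after POEM make up b·s of the total: 5/23 = 22% of positives at b = 10%, and 20/32 = 62.5% at b = 40%. That is a count of carried-over cases. It overstates the effect of baseline, because 20% of those patients would be positive anyway at the assumed onset rate.

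**Step 3: how far a comparison of pathology groups could be affected.** Assume two groups of 25 (the planned 50, split equally), new onset of 20% in both, and an exact two-sided Fisher test at 0.05. Any rejection then arises without a difference in new onset.

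| Baseline >7, by group | Persistence | Observed rates | Probability of P < 0.05 |
|---|---|---|---|
| 20% vs 20% | 50% | 26% vs 26% | 2.2% |
| 20% vs 20% | 100% | 36% vs 36% | 2.7% |
| 10% vs 30% | 50% | 23% vs 29% | 3.7% |
| 10% vs 40% | 50% | 23% vs 32% | 5.7% |
| 10% vs 30% | 100% | 28% vs 44% | 15% |
| 10% vs 40% | 100% | 28% vs 52% | 33% |

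At 50% persistence the false-positive probability stays near the nominal level even with unequal baselines, although the observed rates still differ by 6 to 9 points. Material distortion of the test needs both high persistence and a large baseline difference between pathology groups.

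**The case against.** The strongest reply is that this is an argument from silence in a very short protocol. Baseline data are mentioned but not itemised, and the list in the research design section is plainly incomplete, since it omits even the preoperative Eckardt score. This stands as a limit on certainty: a reader might infer that GerdQ is never taken before POEM, but the documents support only that none is specified. If one is taken, the sponsor need only say so and use it.

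Second, section 4.2 defines presence during follow-up, which is a legitimate measure of post-treatment status. It makes no claim of new onset or of causation by POEM, and the primary end point is also defined by follow-up status alone. The mention of postoperative reflux in section 3.4 is a separate sentence and may be purely a matter of timing. This stands too. It does not remove the problem of interpretation when that status is related to pathology by an unadjusted test.

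Third, the documents do not give the items of GerdQ, so they do not establish that the regurgitation and retrosternal pain scored before POEM would raise it above 7. For this reason carry-over is stated as possible, not as shown. The preoperative Eckardt score does not settle it either way: it is a different instrument, and the end point does not use it.

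Fourth, the effect is confined to one component of the secondary outcomes. That is correct. However, section 4.2 joins the components with an or, so if it is read as a composite, GerdQ alone can make a patient positive.

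**Conclusion.** The point holds in a limited form. As written, the plan cannot separate persisting from new symptoms in the GerdQ component, and a relation between that component and pathology could partly reflect differences present before POEM. Under the stated assumptions baseline status adds 3 to 12 percentage points to an observed rate of 23% to 32%. The true size is unknown.

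Three stronger readings are not supported. It does not follow that up to about 62% of reflux events would be an artefact: that figure counts every persistent case, on assumed inputs. Nor does it follow that a pathology-reflux finding would be spurious; that would take high persistence together with unequal baselines, and the documents show neither. Nor does the gap extend to the esophagitis component, which is screened at entry, or to the primary outcome, for which a preoperative Eckardt score is specified.

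This is a worthwhile, inexpensive improvement to a secondary end point and no threat to the main objective.

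**What to change.** 1. Record GerdQ preoperatively at the same contact as the Eckardt score, and list it in section 3.1.1. If it is already among the unlisted baseline data, say so.
2. Analyse follow-up GerdQ, as the score or as >7, adjusted for the baseline score, in all patients with a baseline value. On the assumed rates there would be only 50 × 0.23 = 11.5 to 50 × 0.32 = 16 positive patients, so the continuous score makes better use of the data than the dichotomy.
3. Report the symptom and endoscopic components separately.
4. Show new-onset GerdQ >7 among patients at 7 or less before POEM only as a supplementary analysis. On the assumed range it drops 50 × 0.10 = 5 to 50 × 0.40 = 20 of the 50 patients, and it says nothing about reflux in those patients.

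Cost: one short questionnaire at a contact that already takes place. Sample size and visits do not change. Patients already enrolled without a baseline GerdQ cannot enter the adjusted analysis and should be reported separately.

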4.1 Main clinical outcomes

The primary end point event of patients is Eckardt score in 1 month, 3 months, 6 months and 12 months after POEM. Any Eckardt score >3 points are defined as poor prognosis after POEM.

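### With no minimum preoperative Eckardt score and an absolute cut at >3, a patient who enters at 3 or below can be poor prognosis only by worsening; a sensitivity analysis should cover this

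*Combined protocol and SAP*

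**What the plan says.** The objective, in the Research objective section, is "To determine whether there is difference in prognosis of POEM among patients with achalasia of different pathological characteristics". Section 4.1 names the outcome, "The primary end point event of patients is Eckardt score in 1 month, 3 months, 6 months and 12 months after POEM", and then the label, "Any Eckardt score >3 points are defined as poor prognosis after POEM". The label takes no account of the score before surgery. Good prognosis is not defined in words, so it has to be read as the complement of poor.

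Section 2.3 has four inclusion criteria: "Patients with achalasia treated in Beijing Friendship Hospital, Capital Medical University", an age range of 18 to 80, "Fit and agree to receive POEM therapy", and signed consent. Neither these nor the exclusion criteria set a minimum Eckardt score. Section 3.1 sets none either: "According to clinical manifestations, endoscopy and high-resolution esophageal manometry, achalasia was diagnosed".

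The preoperative score is collected. Section 3.1.1 states: "The Eckardt score was used to score clinical symptoms based on preoperative dysphagia, regurgitation, retrosternal pain, and reduced body mass". Section 3.4 treats the same instrument as a measure of relief: "Follow-up data were collected, including symptom relief (Eckardt score), reflux symptom score (GerdQ score". No section defines a change from baseline, a percentage reduction or a responder rule. The Data processing and analysis section offers chi-square or Fisher's exact tests for counts and Student's t or Mann-Whitney tests for measurements, with no adjustment for baseline.

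**The concern.** The plan follows patients for symptom improvement (Research content; section 3.4), but the label records only whether the symptom level after POEM exceeds a fixed value. For a patient who starts above 3 the two are linked, because the score must fall to 3 or below for the outcome to be good. For a patient who starts at 3 or below they come apart: standing still is a good outcome, and only deterioration is a poor one.

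This matters for the pathology comparison if a feature goes with milder presenting symptoms. That is conceivable on the plan's own account, since the Background says that subtypes differ in clinical characteristics and in ganglion cells and interstitial cells of Cajal. The group with more low-scoring entrants would then show fewer poor outcomes even if POEM worked equally well in both groups, and nothing in the planned analysis would reveal why.

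**Working it through.** The plan gives no figure to reproduce: the 50 cases in section 2.2 come without an event rate, effect size or power. The check is therefore a reading of the rule, followed by an illustration.

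**The rule applied**
- Preoperative 3, then 3 at all four visits: never >3, so not poor, with zero change.
- Preoperative 2, then 4 at any one visit: poor.

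So low-scoring entrants can still have the event, but only by worsening.

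**Illustration.** All inputs except the 50 cases and the two-sided 0.05 level are assumed.
- Two groups of 25, with and without a feature that has no effect.
- Risk of poor prognosis p = 20% for those who enter above 3.
- Risk r = 0% for those who enter at 3 or below.
- Share f entering at 3 or below: 4% in one group, 30% in the other.

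Observed rate = (1 − f) × p + f × r.
- First group: 0.96 × 0.20 = 19.2%, or 25 × 0.192 = 4.8 patients.
- Second group: 0.70 × 0.20 = 14.0%, or 25 × 0.140 = 3.5 patients.
- Spurious difference: 5.2 percentage points, or 1.3 patients.

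Restricted to patients who enter above 3, both rates are 20% and the difference is zero.

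**Sensitivity to r.** The difference equals (0.30 − 0.04) × (0.20 − r). At r = 0% it is 0.26 × 0.20 = 5.2 points. At r = 10% it is 0.26 × 0.10 = 2.6 points. At r = 20% it vanishes.

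**Second setting.** With p = 30%, r = 0% and shares of 0% and 20%, the rates are 30% and 0.80 × 0.30 = 24%, a difference of 6 points.

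**Chance of P < 0.05 at 25 v 25**, summed over all possible pairs of counts:

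| True rates | Fisher's exact | Uncorrected chi-square |
|---|---|---|
| 20% v 20% | 2.2% | 5.5% |
| 19.2% v 14.0% | 3.6% | 8.3% |

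The imbalance raises the chance of a significant result only slightly.

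**How many patients.** If 5% to 20% of all patients entered at 3 or below (an assumed range), that would be 50 × 0.05 = 2.5 to 50 × 0.20 = 10 of the 50.

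**The case against.** The strongest reply is that the problem may hardly arise. Patients are fit for and agree to POEM, diagnosis rests partly on clinical manifestations, and previously treated achalasia is excluded. All of this makes low preoperative scores less likely. It does not rule them out, and no baseline distribution is given, so the size of the problem stays open.

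Second, the label is not the whole outcome. Section 4.1 also names the score itself at four visits, and the t or Mann-Whitney test could be applied to it. That mitigates but does not resolve the point, because no analysis of change from baseline or adjusted for baseline is specified.

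Third, symptom state after treatment is a legitimate meaning of prognosis, and the objective does not use the word response. This stands, and it is a good reason to keep the all-patient comparison.

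A reader might infer more than the text allows:
- That low-scoring entrants are automatically good outcomes. They are not: one score above 3 at any of four visits makes them poor, and the 0% risk used above is an assumption.
- That a feature linked to mild symptoms will be declared a favourable marker. Under the illustrative figures this would rarely happen.
- That a fall from 11 to 4, labelled poor, shows the same gap. It shows a general property of absolute cuts. That patient starts above 3 and would be labelled poor under the restricted comparison too.
- That the primary comparison must be restricted. With 50 patients and an unknown number removed, that is debatable, and a sensitivity analysis gives the needed check without changing the main population.

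**Conclusion.** The point holds in a limited form. By the text alone, a patient who enters at 3 or below and does not rise above 3 at any visit is counted as good prognosis with or without improvement. If the proportion of such patients differs between pathology groups, the unadjusted comparison can be distorted. The illustrated distortion is about 5 percentage points, or 1.3 patients in groups of 25, and it rests on an assumed equal split, an assumed 20% risk above the cut, no risk at or below it, and a marked imbalance (4% against 30%). It shrinks as any of these is relaxed and is nil if nobody enters at 3 or below. The likely harm is a somewhat biased estimate and a blurred interpretation, rather than a false positive test. The point is worth considering; it does not invalidate the primary outcome.

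**What to change.** Keep the all-patient good/poor comparison. In section 4.1 and the Data processing and analysis section, add three things:

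1. A prespecified sensitivity analysis that repeats the same comparison among patients with a preoperative Eckardt score >3.
2. A table, by pathology group, of the preoperative score distribution and the number entering at 3 or below.
3. A description of those low-scoring patients by change from baseline.

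Suggested wording: *The good/poor prognosis comparison will be made in all patients and repeated, as a sensitivity analysis, in patients with a preoperative Eckardt score above 3. The preoperative score distribution and the number of patients at 3 or below will be reported by pathology group, and the latter will be described by change from baseline.*

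The preoperative score is already collected under section 3.1.1, so enrolment, treatment and visits do not change. The cost is one extra analysis on a slightly smaller and therefore less precise set. If no patient enters at 3 or below, the two analyses coincide.

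### Poor prognosis has no retreatment component, so a patient successfully retreated for achalasia between contacts, scoring 3 or less at all four, is not counted as a failure

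*Combined protocol and SAP*

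**What the plan says.** Section 4.1 sets the primary endpoint and its timing: "The primary end point event of patients is Eckardt score in 1 month, 3 months, 6 months and 12 months after POEM". It then gives the only failure criterion: "Any Eckardt score >3 points are defined as poor prognosis after POEM". Good prognosis is not defined, so it is whatever the rule leaves over.

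Three other places bear on whether later treatment would be known:

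- Research proposal, 1. Research design, describes the data as "including demographic data, drug and surgical treatment data during hospitalization", and the follow-up as "The patients were followed up by telephone at 1, 3, 6, and 12 months for improvement in clinical symptoms".
- Section 3.4 lists the follow-up items: "Follow-up data were collected, including symptom relief (Eckardt score), reflux symptom score (GerdQ score), gastroscopic manifestations, reflux esophagitis, esophagography and esophageal manometry". It fixes the times ("Follow-up collection time is 1 month, 3 months, 6 months and 12 months after POEM") and says what patients are asked: "Patients' symptom improvement and postoperative reflux will be inquired". Further treatment for achalasia is in neither the items nor the questions.
- Section 4.2 and the data processing and analysis section do not mention retreatment.

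The one place that deals with other achalasia treatment is the exclusion list in section 2.3 ("the previously received treatment of achalasia"), which applies at entry.

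**The concern.** The study asks whether muscle pathology relates to the prognosis of POEM. At entry it isolates POEM by excluding patients already treated. After POEM nothing plays the same part. If a patient relapses between contacts and a second treatment works, the next score measures POEM plus that second treatment, yet the rule reads it as a result of POEM alone.

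Such a patient would then sit with the good outcomes in any comparison of pathology by prognosis. Counted failures would fall and the success rate would look better than it is. If missed failures resemble the other failures in their pathology, the contrast between groups would weaken. With 50 patients and simple two-group tests, a few events could carry the result. Retreatment that nobody asks about may also be impossible to recover at analysis.

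**Working it through.** **Inputs from the documents.** Contacts at 1, 3, 6 and 12 months (sections 3.4 and 4.1); failure if Eckardt >3 (section 4.1); 50 patients (section 2.2); two-sided 5% level with chi-square or Fisher tests (data processing and analysis). There is no failure rate, relapse rate, retreatment rate, lag or power calculation, so the plan has no figure of its own to reproduce.

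**Step 1: trace one patient through the rule.** Score 2 at month 6, relapse at month 8, retreatment at month 9, score 1 at month 12, and 3 or less at months 1 and 3. No scheduled score exceeds 3, so the patient is not poor prognosis. Change one fact, so that the patient is still above 3 at month 12 or was already above 3 at month 6, and the rule does count the failure. The gap is therefore confined to relapses that begin and are successfully retreated between two consecutive contacts.

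**Step 2: share of retreated relapses missed, by gap.** Assumptions: onset uniform within the gap; retreatment after a fixed lag; retreatment restores a score of 3 or less by the next contact. A relapse is missed if its onset falls at least one lag before the next contact, so

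missed share = max(0, gap length − lag) / gap length.

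| Gap (months) | Length | Lag 1 month | Lag 2 months | Lag 3 months |
|---|---|---|---|---|
| 0–1 | 1 | 0/1 = 0% | 0% | 0% |
| 1–3 | 2 | 1/2 = 50% | 0/2 = 0% | 0% |
| 3–6 | 3 | 2/3 = 67% | 1/3 = 33% | 0/3 = 0% |
| 6–12 | 6 | 5/6 = 83% | 4/6 = 67% | 3/6 = 50% |

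These are shares of *retreated relapses starting in that gap*. They are not shares of all failures. To convert them one would need the timing of relapses and the chance of retreatment, and the documents give neither.

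**Step 3: what missed events could do (illustration only).** Assume a pathology feature splits the 50 patients 25 v 25, true 12-month failure is 5% v 35%, and the same share m of failures is missed in each group. Expected counted failures = 25 × (0.05 + 0.35) × (1 − m) = 10 × (1 − m). Power is for Fisher's exact test, by full enumeration at two-sided 5%.

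| m | Counted failures | Power |
|---|---|---|
| 0 | 10.0 | 0.70 |
| 10% | 9.0 | 0.63 |
| 25% | 7.5 | 0.48 |
| 50% | 5.0 | 0.19 |

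One patient can matter: 1 v 7 failures gives p = 0.049, and 1 v 6 gives p = 0.098. The row m = 0 is as compatible with the documents as the others.

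**The case against.** The strongest reply is that the documents do not show that any patient would be affected. That stands. The number may be zero, and every percentage above rests on assumptions.

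Three further replies stand in part:

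- *The data lists are not exhaustive.* Both the design section and section 3.4 introduce their lists as examples. A reader might infer that treatment is recorded during the hospital stay and nowhere else; the text does not say so. It supports only that no section provides for recording later treatment. Even if it were recorded, section 4.1 would give it no role.
- *The rule speaks of any score above 3*, which could take in an unscheduled score made at retreatment. But no unscheduled assessment is planned, and the sentence before the rule ties the endpoint to the four times.
- *Endoscopy, esophagography and manometry are also in follow-up* and might reveal a second treatment. None of them enters the poor-prognosis rule.

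Two stronger readings are tempting and should be resisted. One is that the clearest failures are moved to the good group. The documents do not support this: persistent failures, failures still waiting for treatment at a contact, and unsuccessful retreatments are all captured. The other is that a definite part of the events is lost, say 1 or 2 of an assumed 5. Nothing links the shares in the Step 2 table to such a count. Even on that assumption, if missed failures resemble the others, the mean pathology difference between prognosis groups would shrink by only 1/46 to 2/47, about 2–4%. The main cost would be lost events and precision.

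**Conclusion.** The point holds in a conditional form. Applied as written, the rule gives the wrong label to a patient who relapses, is successfully retreated between two contacts and scores 3 or less at all four. This is a consequence of a stated definition, not just missing detail. A reader might infer that everyone retreated between contacts is classed as a good outcome; that does not follow, because a score above 3 at any contact is enough for poor prognosis.

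The direction is towards fewer counted failures. The size is unknown. Exposure is greatest in months 6–12, the longest gap, where half or more of retreated relapses would be missed at every lag considered. In the earlier gaps the share can be zero. These shares depend on uniform onset, a fixed lag of 1 to 3 months and successful retreatment. The power figures depend also on the assumed even split, failure rates and equal missed shares. The plan should be amended because the remedy is cheap and the information may not be recoverable later, not because a large bias has been shown.

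**What to change.** Three linked edits:

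1. **Section 3.4:** at each existing contact, ask about any further treatment for achalasia since POEM, and record its type and date.
2. **Section 4.1:** define poor prognosis as an Eckardt score above 3 at 1, 3, 6 or 12 months, or any further endoscopic, surgical or injection treatment for achalasia after the index POEM and up to 12 months.
3. **Data processing and analysis:** state that Eckardt scores obtained after such treatment are not used as evidence of good prognosis.

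Counting retreatment as failure is one way to handle it. The sponsor should fix in advance which treatments qualify, and say explicitly whether drug treatment does.

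The cost is one extra question per contact, short additions to three sections, and possibly a slightly lower reported success rate. No visit, procedure or patient is added. The change concerns the definition and recording of the outcome only and proposes no rule on when or how patients should be treated.
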